1.1. Synopsis

A parallel group treatment, phase 3, blinded, 2-arm study to investigate facial pain improvement with twice-daily use of a novel device combining acoustic vibration with oscillating expiratory pressure compared with a sham device in male and female participants ≥ 18 years of age with sinus pain/headache lacking objective evidence of sinonasal inflammation.

Rationale:

Sinus headache is a widely prevalent chronic disabling condition associated with marked impairments in quality of life. Patients commonly use the term sinus headache to refer to the concept of facial pain/headache originating in the sinonasal or facial region. However, studies have demonstrated that most patients with a chief complaint of sinus headache present without objective evidence of sinonasal inflammation and that symptoms are often related to a primary headache disorder.¹⁻⁴ Headache disorders are an almost universal human experience. Migraine is the third most prevalent disorder and the seventh highest cause of disability worldwide. The direct and indirect socioeconomic costs of headache are estimated at 14 billion dollars per year. Embedded in the sinus headache patient population is a large group of patients with primary headache disorders. Therefore, much of the therapeutic investigation aimed at treatment of sinus headaches has mirrored the more established primary headache literature. Several studies evaluating empiric treatment of sinus headache patients have demonstrated that a majority of patients improve with triptan therapy.⁵⁻⁷ Perhaps the best study, published in 2007, is a multi-center (26 centers in the United States) randomized, double-blinded, placebo-controlled investigation of sumatriptan for treatment of sinus headaches.⁸ Patients with sinus headache fulfilled IHS criteria for migraine, were without active or recent evidence of sinusitis, and had no prior treatment with migraine medications. A statistically significant benefit over placebo was noted with a single 50-mg dose of sumatriptan. Sixty-nine percent and 76% of patients treated with sumatriptan had a positive headache response compared with a placebo response of 43% and 49% at 2 and 4 hours, respectively.

Just as efficacy for triptans was first demonstrated and popularized in the primary headache literature before utilization in sinus headache studies, medical devices are following a similar trend with the recent advent of transcutaneous stimulation devices.⁹ Recently, two studies investigating use of acoustic vibration with oscillating expiratory pressure applied to the nasal cavity for treatment of nasal congestion were performed looking at cohorts of patients with complaint of congestion.^{10,11} One study demonstrated a significant improvement in objective measures of nasal obstruction and both demonstrated improvements in subjective measures of obstruction. Of note, in both studies, investigators noted improvements in facial pain/pressure. We recently conducted an open label trial to determine if simultaneous administration of acoustic vibration and oscillating expiratory pressure (using Sinusonic device) affects the severity of facial pain among patients with complaint of sinus headache. Twenty-nine patients (mean age 49 years, 55% female) completed our preliminary study without any major adverse events. At the 4-week follow-up, facial pain visual analog scale (VAS)⁵ improved from mean standard deviation(SD) of 59.6+/-15.7 to 34.6+/-21.7($p<0.001$) and approximately 70% of patients achieving a minimal clinically important difference (MCID) across all pain metrics. Eighty-six percent of subjects would use device again and recommend it to others. As the next step, we propose a randomized controlled trial. Preliminary data demonstrates that the device is low-risk, with high patient satisfaction, and patients are able to perform the intervention at home with ease.

Table 1: Objectives and Endpoints

Objectives	Endpoints
Primary	
 To assess relative improvements in facial pain/pressure after 8-weeks of twice daily use of the SinuSonic device compare to a sham device
	
 Facial pain visual analogue scale (0-10) (1-week recall period) Facial pain visual analogue scale (0-10) (immediate 5-minute post use recall) Brief Pain Inventory-Short Form
Secondary	
 Safety data Device use satisfaction Nasal obstruction
	
 Percent achieving a minimal clinically important difference Adverse events reported via questionnaire (pain, epistaxis, etc.) Percentage willing to use again and recommend device to others Nasal obstruction symptom evaluation (NOSE) Score change

Overall Design:

This is a parallel, placebo-controlled multicenter randomized trial. The study population will consist of healthy volunteers with sinus headache/pain lacking objective evidence of chronic sinusitis. This will be a single-blinded study blinded to the participants. Because this study will involve minimal intervention from the investigators (i.e. participants will fill out surveys remotely), there will be minimal influence from the investigators and analysts end. Participants will be randomized to the treatment or the sham-placebo arm and the device they received (either device or sham), will be recorded in a secure database. Following screening, investigational intervention assignment will be performed by randomization in a 1:1, investigational device: sham ratio. Data will be collected and stored in an electronic data storage system.

Brief Summary:

The purpose of this study is to measure facial pain/pressure with a novel device using acoustic vibrations with oscillating expiratory pressure compared with a sham device in participants with sinus pain/headache lacking objective evidence of sinonasal inflammation.

Study details include:

- The study duration will be up to 12 months.
- The treatment duration will be up to 8 weeks.

- The visit frequency will be 0 visits. Participants will fill out questionnaires fielded via an electronic data capture system at 1 week, 2 weeks, 3 weeks, and 4 weeks of device use.

[figure not shown]
Number of Participants:

Approximately 120 participants will be screened to achieve 60 enrolled.

A maximum of 60 participants will be enrolled

Study Arms and Duration:

The total duration of study participation with screening, run-in (i.e., delivery of device), and device use is 11 weeks. Participants will use the investigational or sham device for 2 minutes, twice-daily for the entire 8-week study duration.

Data Monitoring/Other Committee:**1.2. Schema**

1.3. Schedule of Activities (SoA)

Procedure	Screening (up to 3 weeks before Day 1)	Baseline (up to 3 weeks before Day 1)	Intervention Period (8 weeks)					E/D	Notes E/D = Early Discontinuation
			Day 1 +/- 3 Days	Week 2 +/- 3 Days	Week 4 +/- 3 Days	Week 6 +/- 3 Days	Week 8 +/- 3 Days		
Informed consent	X								
Inclusion and exclusion criteria	X								Recheck clinical status before randomization and/or first dose of investigational intervention.
Demographics	X								
Medical history (includes substance use)	X								Substances: drugs, alcohol, tobacco, and caffeine
Current medical conditions	X								
Randomization		X							
Study intervention			X	X	X	X	X		

Procedure	Screening (up to 3 weeks before Day 1)	Baseline (up to 3 weeks before Day 1)	Intervention Period (8 weeks)					E/D	Notes E/D = Early Discontinuation
			Day 1 +/- 3 Days	Week 2 +/- 3 Days	Week 4 +/- 3 Days	Week 6 +/- 3 Days	Week 8 +/- 3 Days		
AE review				←=====→					
SAE review: Including solicited administration-site events if applicable: pain or bleeding				←=====→				X	Pain Epistaxis
Device deficiencies			←=====→					X	
Concomitant medication review		X							

Procedure	Screening (up to 3 weeks before Day 1)	Baseline (up to 3 weeks before Day 1)	Intervention Period (8 weeks)					E/D	Notes E/D = Early Discontinuation
			Day 1 +/- 3 Days	Week 2 +/- 3 Days	Week 4 +/- 3 Days	Week 6 +/- 3 Days	Week 8 +/- 3 Days		
Efficacy questionnaire assessment: • VAS facial pain (1 week recall)	X		X	X	X	X	X		
Efficacy questionnaire assessment: • BPI-SF		X	X	X	X	X	X		
NOSE		X					X		
Device use satisfaction questionnaire								X	

2. Introduction

Sinusonic is an FDA registered novel medical device employing simultaneous acoustic vibrations and positive expiratory pressure to the nasal cavity that has been studied for management of nasal congestion and, more recently, sinus headache.

Sinus headache is a widely prevalent chronic disabling condition associated with marked impairments in quality of life. Patients commonly use the term sinus headache to refer to the concept of facial pain/headache originating in the sinonasal or facial region. However, studies have demonstrated that most patients with a chief complaint of sinus headache present without objective evidence of sinonasal inflammation and that symptoms are often related to a primary headache disorder.⁴ Headache disorders are an almost universal human experience. Migraine is the third most prevalent disorder and the seventh highest cause of disability worldwide. The direct and indirect socioeconomic costs of headache are estimated at 14 billion dollars per year. Embedded in the sinus headache patient population is a large group of patients with primary headache disorders. Therefore, much of the therapeutic investigation aimed at treatment of sinus headaches has mirrored the more established primary headache literature. Several studies evaluating empiric treatment of sinus headache patients have demonstrated that a majority of patients improve with triptan therapy.⁵⁻⁷ Perhaps the best study, published in 2007, is a multi-center (26 centers in the United States) randomized, double-blinded, placebo-controlled investigation of sumatriptan for treatment of sinus headaches.⁸ Patients with sinus headache fulfilled IHS criteria for migraine, were without active or recent evidence of sinusitis, and had no prior treatment with migraine medications. A statistically significant benefit over placebo was noted with a single 50-mg dose of sumatriptan. Sixty-nine percent and 76% of patients treated with sumatriptan had a positive headache response compared with a placebo response of 43% and 49% at 2 and 4 hours, respectively.

Just as efficacy for triptans was first demonstrated and popularized in the primary headache literature before utilization in sinus headache studies, medical devices are following a similar trend with the recent advent of transcutaneous stimulation devices.⁹ Recently, two studies investigating use of acoustic vibration with oscillating expiratory pressure applied to the nasal cavity for treatment of nasal congestion were performed looking at cohorts of patients with complaint of congestion.^{10,11} One study demonstrated a significant improvement in objective measures of nasal obstruction and both demonstrated improvements in subjective measures of obstruction. Of note, in both studies, investigators noted improvements in facial pain/pressure.

We recently conducted an open label trial to determine if simultaneous administration of acoustic vibration and oscillating expiratory pressure (using Sinusonic device) affects the severity of facial pain among patients with complaint of sinus headache. Twenty-nine patients (mean age 49 years, 55% female) completed our preliminary study without any major adverse events. At 4-weeks follow-up, facial pain visual analog scale (VAS) improved from mean standard deviation(SD) of 59.6+/-15.7 to 34.6+/-21.7(p<0.001) and approximately 70% of patients achieving a minimal clinically important difference (MCID) across all metrics. Eighty-six percent of subjects would use device again and recommend it to others. As the next step, we propose a randomized controlled trial. Preliminary data demonstrates that the device is low-risk, with high patient satisfaction, and patients are able to perform the intervention at home with ease.

In regards to device use, the device comes with a clear plastic tab at the base of the device. This tab must be removed prior to device use. For a full session, there is a trigger that must be held down after which

subjects should breathe in and out through their nose with a normal amount of force and speed. A gentle humming will be felt and heard and during exhalations, a fluttering sound will be appreciated. After a full session of use (2 minutes), the device will go into a rest mode for 6 minutes.

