2.3.3. Overall Benefit Risk Conclusion

Taking into account the measures taken to minimize risk to participants participating in this study, the potential risks identified in association with the SinuSonic device are justified by the anticipated benefits that may be afforded to participants with Sinus headache.

3. Objectives, Endpoints, and Estimands

Objectives	Endpoints
Primary	

 To determine superiority of SinuSonic intervention versus control in treatment of facial pain for patients with complaint of sinus headache that lack objective evidence of sinonasal inflammation 	
 Change in facial pain visual analogue scale at 8 weeks Change in Brief Pain Inventory Short Form at 8 weeks
Secondary	

 To determine safety of device use 	
 Number and percent of subjects reporting pain with device use Number and percent of subjects reporting epistaxis Change in Nasal Obstruction Symptom Evaluation (NOSE) Score at 8 weeks
Tertiary	

 To determine device use satisfaction 	
 Number and percent of subjects that would use the device again Number and percent of subjects that would recommend the device to others

Primary estimand

The primary clinical question of interest is:

What is the improvement in facial pain measured by facial pain VAS, and BPI-SF in patients with sinus headache treated with SinuSonic device versus a sham device regardless of discontinuation of investigational intervention for any reason and regardless of initiation of rescue medication or change in background medication.

The estimand is described by the following attributes:

- Population: Patients with complaint of sinus headache lacking objective evidence of sinonasal inflammation of nasal endoscopy or imaging
- Endpoint: change from baseline to 8 weeks in facial pain VAS, and BPI-SF
- Treatment condition:

the investigational interventions regardless of discontinuation for any reason, with or without rescue medication or change in background medication (treatment policy strategy).

- Remaining intercurrent events:

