6.11. Lost to Follow up

A participant will be considered lost to follow-up if the participant repeatedly fails to return for scheduled visits and is unable to be contacted by the study site.

The following actions must be taken if a participant fails to return to the clinic for a required study visit:

- The site must attempt to contact the participant and reschedule the missed visit as soon as possible, counsel the participant on the importance of maintaining the assigned visit schedule and ascertain whether the participant wishes to and/or should continue in the study.
- Before a participant is deemed lost to follow-up, the investigator or designee must make every effort to regain contact with the participant (where possible, 3 telephone calls, and if necessary, a certified letter to the participant's last known mailing address or local equivalent methods). These contact attempts should be documented in the participant's medical record.
- Should the participant continue to be unreachable, the participant will be considered to have withdrawn from the study.

- Site personnel, or an independent third party, will attempt to collect the vital status of the participant within legal and ethical boundaries for all participants randomized, including those who did not get study intervention. Public sources may be searched for vital status information. If vital status is determined as deceased, this will be documented and the participant will not be considered lost to follow-up. Sponsor personnel will not be involved in any attempts to collect vital status information.

7. Study Assessments and Procedures

- Study procedures and their timing are summarized in the SoA. Protocol waivers or exemptions are not allowed.
- Adherence to the study design requirements, including those specified in the SoA, is essential and required for study conduct.
- All screening evaluations must be completed and reviewed to confirm that potential participants meet all eligibility criteria. The investigator will maintain a screening log to record details of all participants screened and to confirm eligibility or record reasons for screening failure, as applicable.
- Procedures conducted as part of the participant's routine clinical management [(eg, blood count, ENT examination)] and obtained before signing of the ICF may be utilized for screening or baseline purposes provided the procedures met the protocol-specified criteria and were performed within the timeframe defined in the SoA.

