8.1. Statistical Hypotheses

The primary objective is to demonstrate that Sinusonic device is superior to Sham control in achieving improvements in facial pain measured by facial pain VAS, and BPI-SF at 8 weeks. Thus, the null hypothesis to be tested in relation to the primary estimand is as follows:

- Null hypothesis: Sinusonic is not different from sham control with respect to the achievement of improvement in facial pain VAS, and BPI-SF at 8 weeks.

The null and alternative hypotheses corresponding to the secondary estimands are as follows:

Secondary objective [1]:

- Null hypothesis: SinuSonic device is not different from Sham control with respect to the achievement of adverse event rate at 8 weeks.

Secondary objective [2]:

- Null hypothesis: Sinusonic device is not different from Sham control with respect to device satisfaction rate at 8 weeks

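### The schedule collects device satisfaction only at early discontinuation, so the 8-week satisfaction comparison would rest on dropouts alone

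*Combined protocol and SAP*

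**What the plan says.** The Schedule of Activities (Section 1.3) has a row for the "Device use satisfaction questionnaire" with a single mark, in the E/D column. The table's own note reads "E/D = Early Discontinuation". Screening, Baseline, Day 1 and Weeks 2, 4, 6 and 8 are blank in that row.

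Section 8.1, secondary objective 2, states: "Null hypothesis: Sinusonic device is not different from Sham control with respect to device satisfaction rate at 8 weeks".

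The endpoint itself is defined twice, both times without a timepoint. The synopsis lists it among the secondary endpoints as "Percentage willing to use again and recommend device to others". Section 3 lists it as tertiary, beginning with "Number and percent of subjects that would use the device again" and adding willingness to recommend the device.

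For timing, the opening of Section 7 sends the reader to the schedule: "Study procedures and their timing are summarized in the SoA". It also makes adherence to the schedule mandatory. The only other general statement on questionnaire timing is in the synopsis, "at 1 week, 2 weeks, 3 weeks, and 4 weeks of device use". That statement does not mention satisfaction and does not reach Week 8.

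**The concern.** A hypothesis about satisfaction at 8 weeks needs answers at 8 weeks from the randomised arms. The schedule asks only those who leave early. Section 8.3.1.1 excludes missing data points, so every completer would drop out of the comparison.

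Two things would be lost. The first is precision, because very few people would answer. The second is more serious: early discontinuation happens after randomisation and may depend on the device received, so the two sets of respondents would not be comparable as randomised groups. A larger number of dropouts would not cure that. The respondents would also not be 8-week respondents in any ordinary sense.

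The trial has no scheduled visits according to the synopsis, and questionnaires go out through an electronic system. If that system is built from the schedule, no one on site is placed to notice the gap, and an answer not requested at Week 8 is hard to recover later without recall bias.

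**Working it through.** The plan gives no figure to reproduce here. The point turns on where one mark sits, so the check is first of the table and then of the consequence.

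**1. Position of the mark.** The schedule has 10 columns: Procedure, Screening, Baseline, Day 1, Week 2, Week 4, Week 6, Week 8, E/D, Notes. The four rows in the last block of the table each have 10 cells:

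| Row | Marked at | Agrees with the text? |
|---|---|---|
| VAS (1-week recall) | Screening, Day 1, Weeks 2, 4, 6, 8 | Follow-up times agree with Section 4.1 |
| BPI-SF | Baseline, Day 1, Weeks 2, 4, 6, 8 | Agrees with Section 4.1 |
| NOSE | Baseline, Week 8 | Agrees with the 8-week change in Section 3 |
| Satisfaction | E/D only | Conflicts with Section 8.1 |

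The NOSE row directly above has its last mark at Week 8, one column to the left of the satisfaction mark. E/D is a genuine separate column: SAE review and device deficiencies are also marked there. A shift confined to the satisfaction row is therefore unlikely, though it cannot be excluded without the original table.

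**2. Other timing.** No other section schedules this questionnaire at Week 8 or for completers.

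**3. Number of respondents.** Inputs: 60 participants (Section 8.4) and 1:1 allocation (Section 6.4), so 30 per arm. The documents give no discontinuation rate, so d below is an assumption. Respondents = 60 × d, and half of that per arm if dropouts split evenly:

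| Assumed d | Total respondents | Per arm |
|---|---|---|
| 5% | 3 | 1.5 |
| 10% | 6 | 3 |
| 20% | 12 | 6 |
| 30% | 18 | 9 |

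With a Week 8 mark as well, up to 60 could answer, 30 per arm.

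**4. Precision, for illustration at d = 10%.** These are exact (Clopper-Pearson) 95% intervals for the positive rate in one arm. When all n answers are positive the lower limit is 0.025^(1/n).

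- 3 of 3 positive: 0.025^(1/3) = 0.292, so 29% to 100%.
- 26 of 30 positive (86.7%): 69% to 96%.

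The counts are hypothetical. The second is close to the 86% reported for the pilot and serves only as a plausible full-sample value.

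**5. Ability to test.** The plan names no test for proportions, so Fisher's exact test is assumed. With 3 per arm, the most extreme table is 3/3 against 0/3. There are C(6,3) = 20 equally likely allocations and 2 are this extreme, so the two-sided p = 2/20 = 0.10. No result could reach 0.05.

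**The case against.** The strongest reply is that this is an obvious slip. Section 8.1 fixes the time at 8 weeks, the endpoint definitions are not restricted to people who stop, and nothing suggests that the sponsor chose to survey only dropouts. That is probably right about the intent. It does not remove the problem, because no sentence in the plan corrects the schedule, and Section 7 makes the schedule the working document.

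A second reply is that the case rests on one mark in a table read from PDF. The same schedule has another loose mark: the AE and SAE arrows begin in the Week 2 cell, while Section 7.3.1 collects those events from the start of the intervention. This stands as a reason to confirm the mark in the original. It does not outweigh the three neighbouring rows, which line up with the text.

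A third reply is that little depends on satisfaction. Section 3 calls it tertiary, and in the order of Section 8.1 it comes last, so under Section 8.1.1 it is formally tested only if the preceding hypotheses are rejected. This also stands, and it limits the importance: no primary or safety result is affected. Nor does the plan propose a formal comparison with the pilot, which was open label, single arm and followed for 4 weeks, so the case should not lean on that.

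Finally, 10% is only one possible dropout rate, and nothing in the documents shows how early leavers would answer. Across 5% to 30% the number of respondents stays between about 3 and 18 of 60, and the selection problem is present at every rate.

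**Conclusion.** The concern holds. As written, the schedule gives the satisfaction questionnaire only to participants who discontinue early, while Section 8.1 tests satisfaction between arms at 8 weeks. The two cannot both be followed.

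The comparison would have about 3 to 18 respondents out of 60, on assumed discontinuation of 5% to 30% with everyone who stops answering, and those respondents would be selected after randomisation. At 3 per arm it could not reach significance with an exact test.

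The conclusion assumes that the mark sits where the extracted table shows it. It should be corrected before questionnaires go out, but it is not critical, since satisfaction is a secondary or tertiary endpoint.

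**What to change.** Confirm the mark in the original schedule. Then mark the satisfaction questionnaire at Week 8 for every participant, keep the mark at early discontinuation, and check that the electronic system sends it at both points.

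State in the analysis section that the comparison uses all randomised participants who answer at either point, by assigned arm, with the early-discontinuation answers also shown separately. The added mark is what resolves the contradiction. The separate display is a recommendation that lets the reader see how far early leavers influence the result.

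In the same edit, give the endpoint its 8-week timepoint in the synopsis and Section 3, and settle whether it is secondary or tertiary.

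The cost is one mark in the schedule, two or three items added to the existing Week 8 electronic questionnaire, and a few lines of text. Sample size and clinical management are unchanged.
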